Seattle Children's Hospital

[name]

[contact]

[contact]

Study Co-Chair

[name], DO, PhD

Neurology

Seattle Children's Hospital

[name]

[contact]

[contact]

Study Statistician

[name]

Seattle Children's Research Institute

[name]

[name]

[contact]

[contact]

PROTOCOL SYNOPSIS

TITLE	Phase 1 study of ABI-009 (nab -rapamycin) for Surgically-Refractory Epilepsy (RaSuRE)
SPONSOR-INVESTIGATOR	[name], PhD Seattle Children's Hospital [name]
FUNDING ORGANIZATION	AADi Bioscience, Inc. Seattle Children's Hospital
NUMBER OF SITES	1
RATIONALE	Seizures that are refractory to both medical and surgical therapy increase the risk of morbidity and mortality in children with epilepsy. At this point in time, options for these children are sparse and suboptimal. This hypothesis-driven phase 1 study aims to evaluate the use of a mammalian target of rapamycin [mTOR] inhibitor, ABI-009, in this subset of challenging participants. The underlying hypotheses being tested in trial are: (1) ABI-009 is a safe and well-tolerated medication in children who have medically-refractory epilepsy and have failed epilepsy surgery, and (2) The addition of ABI-009 therapy to the current clinical standard of continued antiepileptic medications results in improved epilepsy control. This is unique among trials of anti-epileptic medications in that it also studies mTOR inhibition in a non-Tuberous Sclerosis Complex (TSC) specific population for whom few additional effective therapies exist.
STUDY DESIGN	This is a prospective, single-center, phase 1 safety study to investigate the safety, tolerability, seizure control, and quality of life in participants with medically-refractory epilepsy who failed epilepsy surgery. These participants will have continued seizures despite being at least 3 months post-epilepsy surgery (resective surgery with an intent to cure). Upon enrollment, participants will be continued and observed on their pre-existing, clinically prescribed antiepileptic drug (AED) regimen for 1 month. At the 1-month mark, participants will receive weekly ABI-009 intravenously at different dose levels in cohorts of 3 participants each using the standard 3+3 dose-finding design. ABI-009 will be continued for a total of 3 weeks. ABI-009 will then be discontinued and the participants will be observed for an additional 3 months. We intend an expansion of the maximum tolerated dose (MTD) cohort to an estimated additional 6 participants for a maximum possible enrollment of 18 participants.
DURATION OF SUBJECT PARTICIPATION	Participants will be on study for about five months. Initial control period: 1 month Dosing period: 3 weeks

AND DURATION OF STUDY	Follow-up: 3 months
PRIMARY OBJECTIVE	
Safety and Tolerability:
 
 ▪ Determine dose-limiting toxicities (DLTs) and MTD of ABI-009 in participants with surgically-refractory epilepsy ▪ Record the adverse events (AEs) and document their severity with ABI-009 dosing for medically intractable epilepsy that has failed surgical resection, administered in conjunction with their pre-existing AED regimen. Record the compliance of families with medication and record the number of participants that withdraw from study either voluntarily or by necessity secondary to AEs. ▪ Columbia-Suicide Severity Rating Scale (C-SSRS) serious suicidal ideation score stays below a 4 rating.
SECONDARY OBJECTIVES	
Efficacy and Quality of Life:
 
Efficacy is defined as the change from in seizure frequency between baseline and follow-up, expressed as percentage reduction in seizure rate (reduction in seizure frequency from baseline, calculated as (Baseline frequency [seizures/week] – frequency at follow-up [seizures/week])/Baseline frequency [seizures/week]) and median percentage reduction in seizure frequency. Treatment response rate will be defined as the proportion of participants achieving at least a 25% reduction in seizure frequency from baseline. Seizure frequency will be defined as the ratio between the number of seizures and the number of days on which seizure information was known within the same period of time (for either baseline or maintenance phase). Additional secondary endpoints will include frequency of seizure-free days during the maintenance period, seizure-free rate (participants remaining seizure free during the entire maintenance period), and rapamycin blood level–response relationship analysis.
 
Evaluate quality of life indices for participants before, during, and after dosing with ABI-009 in conjunction with pre-existing AED regimens.

NUMBER OF PARTICIPANTS	Up to 18
PARTICIPANT SELECTION CRITERIA: Inclusion Criteria	
Inclusion Criteria:
 
 1. Written informed consent (and assent when applicable) obtained from participant or participant's legal representative 2. Willingness and able to adhere to the study visit schedule and other protocol requirements 3. Male or female ≥ 3 and ≤ 26 years of age at Visit 1 
 a. Because no dosing or adverse event data are currently available on the use of ABI-009 in participants <3 years of

age, these young children are excluded from this study.

4. Documentation of a diagnosis of medically intractable epilepsy as defined by the failure of at least 2 appropriately dosed and tolerated AEDs to eliminate all clinical seizures over a 6-month period prior to epilepsy surgery
5. Documentation of resective epilepsy surgery following appropriate presurgical evaluation
6. Documentation of continued clinical seizures that persist at least 3 months following resective epilepsy surgery. In order to proceed with enrollment and study drug initiation, participants must have had >8 seizures in the last 30 days without 2 consecutive weeks of seizure freedom.
7. Documentation that the participant is not a candidate for *or* refuses any additional resective epilepsy surgery
8. Participants must have adequate bone marrow function (ANC $\geq 1,000/\text{mm}^3$, platelet count of $\geq 100,000/\text{mm}^3$, and hemoglobin $\geq 9 \text{ gm/dL}$) before study drug dosing.
9. Participants must have adequate liver function (SGPT/ALT ≤ 5 times ULN and bilirubin ≤ 5 times ULN) before study drug dosing.
10. Participants must have adequate renal function before study drug dosing, defined as: Creatinine clearance or radioisotope GFR $\geq 70 \text{ mL/min}/1.73 \text{ m}^2$ **or** a serum creatinine based on age/gender as follows:

Age	Maximum Serum Creatinine (mg/dL)	
	Male	Female
3 to < 6 years	0.8	0.8
6 to < 10 years	1	1
10 to < 13 years	1.2	1.2
13 to < 16 years	1.5	1.4
≥ 16 years	1.7	1.4

The threshold creatinine values in this table were derived from the Schwartz formula for estimating GFR utilizing child length and stature data published by the CDC.

11. Participants must have a fasting cholesterol level $< 350 \text{ mg/dL}$ and triglycerides $< 400 \text{ mg/dL}$ before starting study drug. In case one or both of these are exceeded, the participant can only be included after initiation of appropriate lipid lowering medication and documentation of cholesterol $< 350 \text{ mg/dL}$ and triglycerides $< 400 \text{ mg/dL}$ before study drug dosing.
12. Participants must have normal oxygen saturation before study drug dosing.
13. The effects of ABI-009 on the developing human fetus at the recommended therapeutic dose are unknown. For this reason and

	
because ABI-009 are known to be teratogenic, participants of child-bearing potential and men must agree to use adequate contraception (hormonal or barrier method of birth control; abstinence) prior to study entry, for the duration of study participation, and for 6 months after the last dose of ABI-009. Should a female participant become pregnant or suspect she is pregnant while participating in this study, she should inform her treating physician immediately.
 
 Participants of child-bearing potential must not be breastfeeding or pregnant as evidenced by a negative pregnancy test before enrollment and before initiating study drug dosing.

PARTICIPANT SELECTION CRITERIA: Exclusion Criteria
	
Exclusion Criteria:
 
 For females of child bearing potential: 
 Positive pregnancy test at any visit or Lactating or Unwilling to practice a medically acceptable form of contraception (acceptable forms of contraception: abstinence, hormonal birth control, intrauterine device, or barrier method plus a spermicidal agent), unless surgically sterilized or postmenopausal during the study Participant has any other condition that, in the opinion of the Site Investigator/designee, would preclude informed consent or assent, make study participation unsafe, complicate interpretation of study outcome data, or otherwise interfere with achieving the study objectives. Participant has received immunization with attenuated live vaccines within 1 week of study entry and/or is planning to receive immunization with attenuated live vaccines during study period. Examples of live vaccines include intranasal influenza, measles, mumps, rubella, oral polio, BCG, yellow fever, varicella and TY21a typhoid vaccines. Close contact with those who have received attenuated live vaccines should be avoided during dosing with ABI-009. Participant tests positive for Hepatitis C antibodies or the Hepatitis B antigen. HBsAg and HCVAb blood test must be done at screening (HBsAg only needs to be screened in patients who have not received the full complement of Hepatitis B immunizations). Alternatively, if the patient has received the complement of Hepatitis B immunizations and documentation is provided, this would suffice. A known history of HIV seropositivity. HIV-positive patients on combination antiretroviral therapy are ineligible because of the

	
potential for pharmacokinetic interactions with ABI-009. In addition, these patients are at increased risk of lethal infections when treated with marrow-suppressive therapy.
 
 6. Participant is receiving chronic, systemic treatment with corticosteroids or another immunosuppressive agent. Note: Patients that are currently using inhaled, intranasal, ocular, topical or other non-oral or non-IV steroids are not necessarily excluded from the study but must be discussed with the study chair. 7. Participant has been previously treated with a systemic mTOR inhibitor for epilepsy. Skin cream use with rapamycin or everolimus, however, is permitted. 8. Participant has a known hypersensitivity to human albumin, ABI-009, or other rapamycins (e.g. sirolimus, everolimus, temsirolimus). 9. Participant is receiving any other concurrent anticancer or investigational therapy. Participants will be permitted to enroll in the study after a 30-day washout of previously used investigational drugs. 10. Participant has any clinically significant unrelated systemic illness that would compromise their ability to tolerate protocol procedures. 11. Participant is unable to return for treatment and follow-up visits to assess toxicity to the study drug. 12. Participant has an uncontrolled intercurrent illness including, but not limited to, ongoing or active infection, symptomatic congestive heart failure, unstable angina pectoris, cardiac arrhythmia, active lung disease, or psychiatric illness/social situations that would limit compliance with study requirements. 												
TEST PRODUCT, DOSE, AND ROUTE OF ADMINISTRATION	
For dose finding, ABI-009 will start at 5 mg/m²/dose IV, once a week for three weeks, in cohorts of 3 participants each using the standard 3+3 dose-finding design.
 
  
 Dose-levels	ABI-009 in mg/m²	
   
 -2	1	
 
 -1	2.5	
 
 1	5	
 
 2	10	
 
 3	20	
  
 
Escalation to the next dose level with a new cohort of 3 participants will occur after no DLT is observed. There will be no intra-participant dose escalation allowed. If a DLT occurs in a cohort, an additional 3 participants will be recruited to the cohort. If no further DLTs occur,
	Dose-levels	ABI-009 in mg/m ²	-2	1	-1	2.5	1	5	2	10	3	20
Dose-levels	ABI-009 in mg/m ²												
-2	1												
-1	2.5												
1	5												
2	10												
3	20												

	
then a new cohort of 3 participants at the next higher dose level can be enrolled. If 2/6 participants at dose level 1 experience a DLT, then that cohort will be closed to further enrollment and 3 participants will be enrolled at the next lower dose level, and so on. The MTD is the highest dose level in which ≤ 1 participant has a DLT.
 
Once the MTD has been determined, the MTD cohort will be opened for an additional 6 participants. These participants will adhere to the identical protocol of the rest of their cohort.
 
Product will be administered IV every seven days for three weeks.

CONTROL PRODUCT, DOSE AND ROUTE OF ADMINISTRATION	
There is no control product for this study. Participants will serve as their own controls by continuing their pre-existing AED regimen for 1 month after enrollment prior to starting dosing with ABI-009. In order to proceed with drug administration participants will have to have had >8 seizures in 30 days without 2 consecutive weeks of seizure freedom.

CONCOMITANT MEDICATIONS	
Allowed: Standard therapy for epilepsy is allowed except for treatments noted in the prohibited medications section below. Pre-existing AEDs must not be titrated while participants are enrolled in the study, unless the dose change is solely to address subtherapeutic levels as determined by the treating neurologist. Rescue medication is allowed for prolonged seizure event or cluster of seizures.
 
Prohibited: The following medication changes are prohibited during participation in the trial, and as such will be considered a protocol violation:
 
 • Any changes in dosage of AED regimen, unless solely to address subtherapeutic levels of AEDs as determined by the treating neurologist. • Any additions or removal of AEDs to the participant's AED regimen during participation unless medically necessary and discussed with investigator
PRIMARY ENDPOINT	
Safety:
 
DLT and MTD
 
Incidence of adverse events and clinically significant abnormal lab values
 
Tolerability:
 
Number of participants withdrawn from study
 
Adherence to prescribed ABI-009 regimen
 
Columbia-Suicide Severity Rating Scale (C-SSRS) serious suicidal ideation score stays below a 4 rating.

SECONDARY	
Efficacy:

ENDPOINTS	
Seizure frequency Percentage reduction in seizure frequency Median percentage reduction in seizure frequency Response rate Frequency of seizure-free days Seizure-free rate Rapamycin blood level–response relationship
 
Other:
 
Quality of life and behavioral index Determine weekly whole blood rapamycin trough levels for three consecutive weeks

STATISTICS Primary Analysis Plan	
Analysis of Primary Endpoints
 
The number of SAEs and AEs will be summarized for each dosing group as follows: (i) The proportion of participants with at least one (S)AE, (ii) The average number of (S)AEs per participant, and (iii) The rate of (S)AEs per participant week of follow-up. Histograms showing the frequency of the number of (S)AEs in each dosing group will be included. Rates of (S)AEs by System Organ Class (SOC) will be presented by treatment group. Poisson regression modeling for count data will be used to derive rate ratios and 95% CIs for each SOC.
 
Safety lab data at each study visit and changes from baseline will be summarized by dosing group. In addition, the following clinical laboratory summaries will be presented by dosing group: (i) the incidence of clinically significant abnormalities at each study visit; and (ii) tables summarizing the frequencies of participants below, within, and above the normal reference ranges at baseline and end of study; and (iii) tables displaying baseline to end of study shifts in each laboratory value (shifts between below, within or above normal range).
 
The number of hospitalization events and proportion of participants hospitalized from baseline to final day of study will be summarized and compared by treatment group. Poisson regression modeling will be used to derive rate ratios and 95% CIs.
 
Study compliance will be assessed via compliance with scheduled weekly infusions.
 
Analysis of Secondary Endpoints
 
Efficacy is defined as the change in seizure frequency between baseline and follow-up, expressed as percentage reduction in seizure rate (reduction in seizure frequency from baseline, calculated as (Baseline frequency [seizures/week] – frequency at follow-up

	
[seizures/week])/Baseline frequency [seizures/week]) and median percentage reduction in seizure frequency. Treatment response rate will be defined as the proportion of participants achieving at least a 25% reduction in seizure frequency from baseline. Seizure frequency will be defined as the ratio between the number of seizures and the number of days on which seizure information was known within the same period of time (for either baseline or maintenance phase). Additional secondary endpoints will include frequency of seizure-free days during the maintenance period, seizure-free rate (participants remaining seizure free during the maintenance period), and rapamycin blood level-response relationship analysis. These endpoints will be analyzed using appropriate statistical tests, such as the test of proportions and time to event analyses.
 
Quality of Life for Children with Epilepsy Parent Form (QOLCE) [1] and Nisonger Child Behavioral Rating Form (NCBRF) [2, 3] scores will be compared using appropriate statistical tests for ordinal data, including Wilcoxon signed rank tests, logistic regression, or contingency tables.

Rationale for Number of Participants	In this phase 1 study, it is estimated that a maximum of up to 18 participants will be required to achieve the MTD; however, MTD could be reached with as few as 9 participants, but also possible that the MTD is not reached in this study. With the MTD expansion cohort, it is estimated that additional 6 participants would bring the maximum number of participants enrolled to 18. A total of up to 18 participants should be enough for a safety and tolerability study in an orphan condition.

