4 STUDY DESIGN

4.1 Study Overview

This is a prospective, single-center, non-randomized open-label phase 1 study to investigate multiple dose levels of ABI-009 for surgically-refractory epilepsy. Up to 18 participants are planned to be enrolled into the study.

The duration of participation for each participant is up to 18 weeks, including a 4-week baseline period to obtain baseline outcome rates, a 3-week active study period and a 12-week follow-up period (see Figure 1). After the baseline period, participants will be started on the assigned dose of ABI-009, given once weekly for a total of 3 weeks. Dose levels to be tested are below:

For dose finding, ABI-009 will be tested in cohorts of 3 participants each using the standard 3+3 dose-finding design. Initial starting dose will be at 5 mg/m²/week.

Table 3: ABI-009 Cohort Dosing Schedule

Dose levels	ABI-009 in mg/m ²
-2	1
-1	2.5
1	5
2	10

3	20
---	----

Escalation to the next dose level with a new cohort of 3 participants will occur after no DLT was observed. There will be no intra-participant dose escalation allowed. If a DLT occurs in a cohort, an additional 3 participants will be recruited to the cohort. If no further DLTs occur, then a new cohort of 3 participants at the next higher dose level can be enrolled. If 2/6 participants at a dose level experience a DLT, then the cohort will be closed to further enrollment and 3 participants will be enrolled at the next lower dose level, and so on. The MTD is the highest dose level in which ≤ 1 participant has a DLT. There will be no intra-participant dose escalation allowed.

Once the MTD has been determined, the MTD cohort will be opened for an estimated additional 6 participants. These participants will adhere to the identical protocol of the rest of their cohort.

Product will be administered IV every 7 days for 3 weeks.

For a detailed review of visits, please see Appendix 1.

Total duration of the study is expected to be about one year.

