11. Participants must have a fasting cholesterol level <350 mg/dL and triglycerides <400 mg/dL before starting study drug. In case one or both of these are exceeded, the participant can only be included after initiation of appropriate lipid lowering medication and documentation of cholesterol <350mg/dL and triglycerides <400mg/dl before study drug dosing.
12. Participants must have normal oxygen saturation before study drug dosing.
13. The effects of ABI-009 on the developing human fetus at the recommended therapeutic dose are unknown. For this reason and because rapamycin is known to be teratogenic, female participants of child-bearing potential and men must agree to use adequate contraception (hormonal or barrier method of birth control; abstinence) prior to study entry and for the duration of study participation. Should a female participant become pregnant or suspect she is pregnant while participating in this study, she should inform her treating physician immediately.
 - a. Participants of child bearing potential must not be breastfeeding or pregnant as evidenced by a negative pregnancy test at enrollment and before study drug initiation.

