10.5 Visit 6: Post-Dosing One-Week Assessment (+/-2 days)

1. Review adverse events.
2. Review epilepsy diary.

3. Investigator opinion regarding seizures recorded: same, worse, somewhat better, better.
4. Record changes to concomitant medications.
5. Perform abbreviated physical examination.
6. Obtain and record vital signs.
7. Collect urine for pregnancy test (if child-bearing potential).
 - a. If positive confirm with blood test
8. Collect blood for clinical laboratory tests (chemistry, hematology).
9. Laboratory assessments as required per the schedule of evaluations
 - c. Complete Blood Count (CBC) with differential and platelet count
 - d. Blood chemistry assessment, including:
 - i. Sodium, potassium, chloride, bicarbonate, calcium, fasting glucose, albumin,
 - ii. Total protein, BUN, serum creatinine.
 - iii. Total bilirubin, AST, ALT, alkaline phosphatase, uric acid, phosphorus,
 - iv. Fasting serum lipid profile (total cholesterol, triglycerides, HDL and LDL)
10. Coagulation assessment, including prothrombin time, partial thromboplastin time, international normalized ratio (PT/PTT/INR)
11. Whole blood rapamycin trough level
12. Administer C-SSRS, QOLCE, and NCBRF

10.6 Follow-up Visits 7, 8, & 9: 30, 60, and 90 Days Post-Dosing (+/-7 days)

1. Review participant diary for compliance and seizure frequency.
2. Safety follow-up labs at Visit 7 per PI discretion following Visit 6 labs.
3. Investigator opinion regarding seizures recorded: same, worse, somewhat better, better
4. Record changes to concomitant medications.
5. Perform abbreviated physical exam (30 days post-doing only).
6. Measure and record height and weight (at final study visit).
7. Obtain and record vital signs (30 days post-dosing only).
8. On final visit (90 days post-dosing) administer C-SSRS, QOLCE and NCBRF

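### Inclusion criterion 13 gives two different end points for contraception: the synopsis runs to six months after the last dose, Section 6.2 stops when participation ends

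*Combined protocol and SAP*

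**What the plan says.** Both copies of inclusion criterion 13 are current text, and both apply to participants of child-bearing potential and to men.

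- **Synopsis, inclusion criterion 13:** contraception is required before entry, throughout participation, "and for 6 months after the last dose of ABI-009". The stated reason is "because ABI-009 are known to be teratogenic".
- **Section 6.2, inclusion criterion 13:** contraception is required "prior to study entry and for the duration of study participation". The stated reason is "because rapamycin is known to be teratogenic".

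Both copies also say that effects on the human fetus at the recommended therapeutic dose are unknown.

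The length of participation after dosing is given in three ways:

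- The synopsis design paragraph says "ABI-009 will then be discontinued and the participants will be observed for an additional 3 months".
- Section 4.1 describes "a 3-week active study period and a 12-week follow-up period".
- The heading of Section 10.6 reads "Follow-up Visits 7, 8, & 9: 30, 60, and 90 Days Post-Dosing (+/-7 days"; Appendix 1 also places Visit 9 at 90 days.

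Exclusion criterion 1c (synopsis and Section 6.3) covers contraception for females of child-bearing potential. It refers only to the study itself, with no period after dosing.

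**The concern.** A single eligibility criterion should have a single end point. Here the copy in the eligibility section drops a post-dose period that the synopsis contains, and no order of precedence is stated. Three consequences follow from the documents.

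- **Eligibility is undetermined for some people.** Agreement to contraception is a condition of entry. Section 6.3 closes by saying that no waivers will be granted, and Section 13 lists failure to meet entry criteria as a protocol violation. Whether a participant who agrees only through the final visit is eligible depends on which copy is read.
- **Counselling could go either way.** The protocol gives site staff no basis for choosing between the two durations.
- **The disputed interval has no other cover.** Pregnancy tests, whether taken from the visit lists in Section 10, the monthly instruction in Section 10.1 or Appendix 1, are not scheduled beyond the final visit. Collection of serious adverse events, which include congenital anomaly, ends with the final visit (Sections 11.2 and 11.2.1). Criterion 13 asks a participant to report a pregnancy only while taking part.

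The subject is one that the protocol treats as a safety matter: it calls the drug or its active substance teratogenic, Section 2.1 reports embryo and fetal toxicity of rapamycin in rats, and enrolment extends to age 26.

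**Working it through.** The protocol states no figure for the difference, so there is none to reproduce. The check is a comparison of text followed by date arithmetic.

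**Step 1. Comparison of the two copies**

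| Element | Synopsis, criterion 13 | Section 6.2, criterion 13 |
|---|---|---|
| Before entry | required | required |
| During participation | required | required |
| After the last dose | 6 months | not mentioned |
| Called teratogenic | ABI-009 | rapamycin |

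The first two rows agree and the last two differ. The concomitant-medication rules (Section 7), the visit lists (Section 10) and exclusion criterion 1c do not restore the post-dose period.

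**Step 2. Size of the difference**

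Inputs: 6 months after the last dose (synopsis), and the time *t* from the last dose to the end of participation (synopsis design paragraph, Section 4.1, Section 10.6). Assumption: one month is 365.25 / 12 = 30.44 days, so 6 months is 182.6 days.

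Difference = 182.6 − *t*

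| Reading of *t* | *t* (days) | Difference (days) | Months |
|---|---|---|---|
| Visit 9 at 90 days | 90 | 92.6 | 3.0 |
| Visit 9 at the early edge of its window | 83 | 99.6 | 3.3 |
| Visit 9 at the late edge of its window | 97 | 85.6 | 2.8 |
| 12 weeks after the last dose | 84 | 98.6 | 3.2 |
| 3 months after the last dose | 91.3 | 91.3 | 3.0 |
| 90 days counted from Visit 6 (one week after the last dose), late edge | 104 | 78.6 | 2.6 |

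The working range is 86 to 100 days. The last row is a less natural reading, and it lowers the bottom of the range to about 79 days.

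Section 4.1 gives a total of up to 18 weeks, although its parts add to 4 + 3 + 12 = 19. Taking 18 weeks as correct, *t* = 126 − 28 − 14 = 84 days, which is the 12-week row again.

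**Step 3. Early withdrawal**

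Section 12.3 lets a participant leave the study at any time. Under Section 6.2 the requirement then ends on leaving. For illustration, *t* = 7 days gives 182.6 − 7 = 175.6 days, or 5.8 months. As *t* approaches 0 the difference approaches 6 months. Stopping the drug early does not by itself have this effect, because Section 12.1 asks such participants to complete the remaining visits.

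**The case against.** The textual conflict is hard to dispute. The fair objections concern what may be built on it.

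- **A reader might infer that Section 6.2 is the operative rule and that participants will stop contraception half-way through the required period.** The documents do not support this. Neither copy is given precedence, and the consent pages are not in the public text, so what participants are told is unknown. The copies are also compatible in one direction: anyone who meets the synopsis meets Section 6.2. The supportable statement is that either duration could be applied.
- **A reader might infer a fixed shortfall of 93 days for everyone.** Section 6.2 contains no 90-day figure; it comes from the visit schedule, which has a window. The three-month figure fits only those who complete follow-up.
- **A reader might infer that fetal exposure in the disputed interval has been shown.** It has not. Section 1.10 gives a half-life of about 60 hours at 45 to 150 mg/m², so 90 days is 90 × 24 / 60 = 36 half-lives. That neither settles the right duration nor reconciles the texts, and neither copy justifies its own duration. It does mean that the point rests on the contradiction and not on demonstrated harm.
- **No analysis of dose-limiting toxicity or maximum tolerated dose is affected.** This stands. The only route to an analysis would be the per-protocol set in Section 15.1.1, if such an eligibility failure were graded a major violation. The protocol does not say, so I give this no weight.
- **Changing criterion 13 alone would not finish the job.** This also stands. Exclusion criterion 1c names no post-dose period and lists different acceptable methods, so it has to be part of the correction.

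**Conclusion.** The point holds as an internal contradiction: inclusion criterion 13 is wrong as written, because its two current copies cannot both be the rule. The difference is about three months (86 to 100 days) for participants who complete follow-up, and approaches six months for someone who withdraws soon after the last dose. These figures assume average-length months, 90 days counted from the last dose, and participation ending at Visit 9 or at withdrawal. The documents do not say how many of the up to 18 participants the criterion would apply to.

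The sponsor should correct it, because it is a no-waiver entry rule that bears on participant safety. It does not threaten the primary analysis. It is not a disagreement with a design decision, since the protocol has not settled on one, and this review takes no position on which duration is right.

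**What to change.** 1. Reconcile inclusion criterion 13 in the synopsis and in Section 6.2 so that one duration appears in both. The choice is the sponsor's.
2. Say whether the end point is tied to the last dose or to the end of participation, so that the rule is clear for someone who withdraws early.
3. Use the same statement of the teratogenic risk in both copies; at present one names ABI-009 and the other rapamycin.
4. Align exclusion criterion 1c, in the synopsis and in Section 6.3, with the reconciled criterion on duration and on the list of methods.
5. Check the consent form and counselling text against the result.

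The cost is a few lines in four places and a check of the consent text, with IRB approval under Section 17.1. If the consent form changes in a way that affects participants, Section 17.3 requires re-consent. Making the wording consistent does not by itself require any change to visits, sample size or analyses.
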